#### *6.6.2.1 Non Adverse Device Event (non ADE)*

Adverse events not related to the use of the investigational medical device. This includes events reported due to the subject condition, not able to be determined to be related to the medical device, or other. A non adverse device event (non ADE) will be considered emergent if the onset of the event is on or after the start of anesthesia for the implant surgery.

#### *6.6.2.2 Device or Procedure Related*

##### Adverse Device Event (ADE)

Adverse events related to the use of the investigational medical device. This includes any adverse event resulting from insufficiencies or inadequacies in the instructions for use, the deployment, the implantation, the installation, the operation, or any malfunctions of the investigational medical device or as a result of a user error or intentional misuse. All ADEs are considered emergent.

##### Unanticipated/Unexpected Serious Adverse Device Event (USADE)

An USADE is an event which by its nature, incidence, severity or outcome has not been identified in the current Risk Management section of the Investigator's Brochure and Instructions for Use. The anticipated/expected adverse events are defined in Section 10.1.4 of the protocol. All USADE are considered emergent.

#### *6.6.2.3 Serious Adverse Event*

A serious adverse event (SAE) is an AE that led to death, led to serious deterioration in health that resulted in life-threatening illness or injury, in permanent impairment of a body structure or body function, in the patient's hospitalization or prolongation of existing hospitalization, in medical or surgical interventions to prevent life threatening illness, or led to fetal distress, fetal death or a congenital abnormality or birth defect.

This includes device deficiencies (DDs) that might have led to a serious adverse event if suitable action had not been taken, or intervention had not been made or if circumstances had been less fortunate.

A serious adverse device event (SADE) is an event that resulted in any of the consequences characteristic of a serious adverse event.

An unanticipated/unexpected serious adverse device effect (USADE) is an unanticipated/unexpected event that resulted in any of the consequences characteristic of a serious adverse event.

### **6.6.3 Clinical Laboratory Evaluations**

Clinical laboratory tests are scheduled at the screening visit (baseline) within 72 hours prior to MVAD® pump implantation, Day 3 and at each post discharge clinical visit. Change from baseline to each visit will be defined as the visit value minus the baseline value. All clinical laboratory test results will be reported in or converted to Standard SI units for analysis. Clinical laboratory results will also be classified as normal (if value is within normal reference range) or abnormal (if value is either below (L) or above the normal reference range (H)).

### **6.6.4 Other Safety Variables**

#### *6.6.4.1 Vital Sign Measurements*

Vital sign measurements (systolic and diastolic blood pressure, mean arterial pressure (MAP), heart rate, respiratory rate, and temperature) are scheduled at the screening visit (baseline), Days 1- 3 post implant, and month 1, 3, 6, 12, 18, and 24. Change from baseline to each visit will be defined as the visit value minus the baseline value. Blood pressure will be managed to maintain MAP as tolerated at  $\leq 85$  mmHg (using an automated cuff method) or  $\leq 90$  mmHg (using the Doppler/cuff method) for at least 3 months after discharge and continue until the subject is medically stable.

#### *6.6.4.2 Hemodynamic parameters*

Hemodynamic parameters are taken at screening visit (baseline), Days 1- 3 post implant, and month 1, 3, 6, 12, 18, and 24. The hemodynamic parameters include central venous pressure, SVO2, right atrial pressure, systolic pulmonary artery pressure, mean pulmonary artery pressure, diastolic pulmonary artery pressure, PCWP, cardiac index, cardiac output, and PVR. All parameters are collected (if possible) at the screening (baseline) visit. Some parameters are available only during right heart catheterization (RHC) monitoring, while others are not available due to RHC monitoring. In addition, some parameters may not be available in some patients who have a VAD implanted. Change from baseline to each visit will be defined as the visit value minus the baseline value.

#### *6.6.4.3 Echocardiogram Parameters*

Echocardiogram parameters are scheduled at screening visit (baseline) and month 1, 3, 6, 12, 18, and 24. The echocardiogram may be obtained within the 6 months prior to the informed consent and used as the screening visit measurements. The echocardiogram parameters

(continuous variables) include set speed (RPM), pump flow (L/min), pump power (Watts), aortic valve opening/min (min), aortic valve opening duration (ms), LVEF (%), LVEDD (cm), LVESD (cm), LVEDV (mL) and LVESV (mL). Change from baseline to each visit will be defined as the visit value minus the baseline value. Other echocardiogram parameters that are categorical variables are aortic valve opening (yes/no), aortic insufficiency (none/mild/moderate/severe), and commissural fusion (yes/no). Additional information recorded includes aortic regurgitation, mitral regurgitation, tricuspid regurgitation, LA dimension, LV wall thickness, and presence of LV thrombus.

#### 6.6.4.4 *Length of Operative Time*

The length of operative time (LOT) will be derived. The length of operative time will be the number of hours from the time of surgery starts for the implant of the device until the time the surgery for implantation of the device is completed.

Length of operative time in hours = time of chest closure – time of chest incision

#### 6.6.4.5 *Length of Initial Hospital Stay*

At discharge, length of stay (LOS) will be collected for LOS overall, LOS in ICU, and LOS in general ward. The length of initial hospital stay based on the LOS overall will be the number of days from the date of hospitalization prior to the device implantation until the date of discharge following device implantation.

Length of hospitalization in days = date of discharge – date of implantation +1

#### 6.6.4.6 *Hospitalization after the Initial Hospitalization for Implant (Re-hospitalization)*

For each patient having a hospitalization (excluding planned procedures) after the initial hospitalization for implant, the length of stay will be collected for LOS overall, LOS in ICU, and LOS in general ward. For each patient, the number of hospitalizations after the initial hospitalization for the device implantation will be tallied. Also for each patient, the cumulative number of days hospitalized after the initial hospitalization for the device implantation will be determined for LOS overall, LOS in ICU and LOS in general ward. All re-hospitalizations will be summarized in the listings (including planned procedures).

#### 6.6.4.7 *Transplantation*

The number of patients with a transplantation will be determined. The denominator will be the number of patients with a device implanted. The time to first transplantation will be calculated as the number of days the transplant occurred after the device implantation.

Time to first transplant in days = date of transplant – date of implantation +1

#### 6.6.4.8 *Explant*

The number of patients with an explant of the device will be tallied. The denominator will be the number of patients with a device implanted. Also the time to explantation of the device will be the number of days from when the explant occurred after the device implantation.

Time to Explant in days = date of explant – date of implantation +1

The reason for explant will also be recorded.

### 6.7 Pharmacodynamics Parameters

Not applicable to this study.

## 7 STATISTICAL METHODS

### 7.1 General Methodology

All analysis will be performed using SAS® Version 9.2 or higher. Data will be summarized using descriptive statistics (number of patients [N], mean, standard deviation [SD], median, minimum, and maximum) for continuous variables and using frequency and percentage for discrete variables.

The primary and secondary efficacy analyses for survival (simple proportion) will be based on the lower bound of the one-sided 95% exact binomial confidence interval exceeding the performance goal. No other hypothesis testing will be performed.

Patient listings of all data from the case report forms (CRFs) as well as any derived variables will be presented.

### 7.2 Adjustments for Covariates

Site effects will be considered for the primary efficacy endpoint using site as a blocking variable. No other covariates are planned to be used in the analyses for this study.

### 7.3 Handling of Dropouts or Missing Data

Patients who are lost to follow-up or who withdraw consent prior to specified relative day will be excluded from both denominator and numerator when computing the simple proportion for the primary endpoint (survival at 6 months) and the first secondary endpoint (survival at 24 months). Patients who are lost to follow-up or who withdraw consent will, however, be eligible for the overall survival analysis.

Transplants, explants for recovery and exchanges (to a device other than the MVAD® Pump) will be eligible for survival analysis with their survival status identified at the time of the

procedure. Death with the MVAD® pump in place is the only event that will be considered a failure.

Patient-years and follow-up time are based on database-driven known time on MVAD® support (including post-exchange time). If a patient is on LVAD support at last known follow-up and a later date of death exists, the date of death must be considered the last follow-up for that patient. The patient is known to be alive and assumed to be on MVAD® support up to the date of death.

If a partial date is reported where the day is missing, then the day will be imputed as the first day of the month unless the month is the same month as the device is implanted then the day will be that of implantation with the month and year remaining the same. If a partial date is reported where the month is missing, then the month will be imputed to January unless the year is the same year as the device is implanted then the month will be that of implantation with the year remaining the same. If a partial date where both the day and month is missing, follow details as stated previously.

Missing data for other parameters will not be imputed for analysis unless defined in Section 6. Censoring for the efficacy endpoints is discussed in Sections 6.4.3.1. Missing adverse event dates will be imputed using partial date imputation rules as previously described in this Section.

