Investigators are not obligated to actively seek AEs in former study participants. However, if the investigator learns of any AE, including a death, at any time after a subject has been discharged from the study, and he/she considers the event reasonably related to the investigational product or study participation, the investigator should promptly notify HeartWare.

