## 12.0 STATISTICAL CONSIDERATIONS

### 12.1 General Statistical Considerations

All data collected in this study will be documented using summary tables and subject data listings. For categorical variables, frequencies and percentages will be presented. For continuous variables, descriptive statistics (n, mean, standard deviation, median, minimum and maximum) will be presented.

Demographic data, including gender, race, age and body surface area (BSA), and baseline assessments (e.g., chronic heart failure (CHF) etiology, cardiovascular history, current hospital admission) will be summarized using frequencies and percentages, or descriptive statistics, as applicable.

Survival will be calculated as actual survival and as estimated survival using the Kaplan-Meier product limit estimate.

Subjects not eligible for endpoint analysis include lost to follow-up and withdrawals prior to endpoint. Subject ineligibility is unexpected, and this protocol addresses it with a planned occurrence rate well under 5%. Transplants, explants for recovery and exchanges (to a device other than the MVAD pump) prior to endpoint will be eligible for endpoint analysis with survival status identified at the time of the procedure. Survival failure is associated with events (death) on the MVAD pump. Endpoint analyses will be performed at 6 months and 24 months.

Any deviations from the planned statistical analyses will be reported with proper justification as a protocol deviation.

Patient-years and follow-up time are based on database-driven known time on MVAD pump support (including post-exchange time). If a subject is on MVAD pump support at last known follow-up and a later date of death exists, the date of death must be considered the last follow-up for that subject. The subject is known to be alive and assumed to be on MVAD pump support up to the date of death.

Statistical analysis will be performed using SAS version 9.1 or higher.

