## 6.4 Efficacy Variables

### 6.4.1 Primary Efficacy Variable – Overall Survival at 6 months

The primary efficacy variable is survival at 6 months after implant expressed as simple proportion of patients alive on the MVAD® pump divided by endpoint eligible patients. The overall survival at 6 months post implant simple proportion point estimate is  $n/N$ ; where  $N$  is the total number of patients included in the analysis set; and  $n$  is the number of patients alive at Relative Study Day 183, lower bound of the 6 month visit.

Patients who are lost to follow-up or who withdraw consent prior to Relative Study Day 183 will be excluded from both denominator and numerator when computing the simple proportion. Patients with transplants, explants for recovery or exchanges (to a device other than the MVAD® Pump) prior to Relative Study Day 183 will be included in the denominator for this analysis, with status identified at time of procedure. If there are any patients who are eligible for analysis but for whom the primary endpoint cannot be assessed, they will be excluded from both denominator and numerator for this analysis.

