### 6.4.2 Secondary Efficacy Variable – Overall Survival at 24 months

The secondary efficacy variable is survival at 24 months after implant expressed as simple proportion (patients alive on the MVAD® pump divided by endpoint eligible patients). The overall survival at 24 months post implant will be presented as a simple proportion; that is, the point estimate will be  $n/N$ ; where  $N$  is the total number of patients included in the analysis set; and  $n$  is the number of patients alive by Relative Study Day 730 (lower bound of the 24 month visit).

Patients who are lost to follow-up or who withdraw consent prior to Relative Study Day 730 will be excluded from both denominator and numerator when computing the simple proportion. Patients with transplants, explants for recovery or exchanges (to a device other than the MVAD® Pump) prior to Relative Study Day 730 will be included in the denominator for this analysis, with status identified at time of procedure. If there are any patients who are eligible for analysis but for whom the primary endpoint cannot be assessed, they will be excluded from both denominator and numerator for this analysis.

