### 6.4.3 Additional Efficacy Variables

#### 6.4.3.1 Overall Survival (Time to Death)

Time to death (TTD) is defined as the time from date of implant until date of death on device (in days). If a patient had a transplant, explants for recovery, exchanges (to a device other than MVAD® Pump) prior to endpoint, and any withdrawal or lost to followup will be censored at the time of this event date. For each patient that remains alive on device, TTD

will be censored at the time of last contact date known to be alive (contacts considered in the determination of last contact date would include but not limited to scheduled visit dates, adverse event date, and last known alive date).

Time to Death (TTD) = Date of event/censor – Date of Implant + 1.

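### Subjects lost or withdrawn before Day 183 or Day 730 leave the survival proportions even when a death by that day is documented, and the documents disagree on how time to death treats that death

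*SAP*

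**What the plan says.** **Survival proportions.** Protocol 12.1: "Subjects not eligible for endpoint analysis include lost to follow-up and withdrawals prior to endpoint". SAP 7.3 words the rule thus, covering both proportions: "Patients who are lost to follow-up or who withdraw consent prior to specified relative day will be excluded from both denominator and numerator". SAP 6.4.1 and 6.4.2 repeat this exclusion, with Day 183 and Day 730 as the respective cut-offs. The trigger is the loss or withdrawal, not whether survival status is known.

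**Later deaths.** Protocol 12.1 covers a subject still supported when last seen, for whom "a later date of death exists, the date of death must be considered the last follow-up for that subject". It adds that such a subject is assumed to have been on MVAD support until then. SAP 7.3 has the same rule. In both documents it follows a sentence about patient-years and follow-up time.

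**Failure.** SAP 7.3 makes death with the pump in place the only failure. Protocol 12.3 likewise ties failure to death on the pump.

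**Time to death.** SAP 6.4.3.1: "any withdrawal or lost to followup will be censored at the time of this event date". Protocol 12.6 also censors these subjects. The programming notes in SAP Appendix 4 set the censoring flag to zero (an event) for all patients who died, with no exception for earlier loss or withdrawal.

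**Current status.** SAP version 2.0, section 5.2, reports an early stop with fewer than 15 subjects enrolled, and replaces summary statistics with case studies.

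**The concern.** Take a subject with the pump running who is lost or withdraws on Day 60 and whose death on Day 120 becomes known. The later-death rule and the failure definition together make this a death on the pump inside the 6-month window. The eligibility rule removes the subject from the proportion. Time to death is either censored on Day 60 or an event on Day 120, depending on which section the programmer follows. No section says which rule takes precedence.

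The documents foresee deaths that come to light late. The later-death rule presupposes them, and protocol 10.0 asks for notification "if the investigator learns of any AE, including a death, at any time after a subject has been discharged from the study", provided the investigator considers the event reasonably related to the product or to participation.

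Excluding a known in-window death takes one failure out of the denominator and nothing out of the numerator, so the estimated proportion can only rise. As designed, the 6-month result was to support CE Mark and the 24-month result long-term use labeling (protocol 6.1).

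**Working it through.** **Inputs.** The performance goals are 70% and 52.5%, the expected rates 85% and 70%. Success requires the one-sided 95% exact lower bound to exceed the goal, and n = 57 plus 3 for attrition gives 60 (protocol 12.3 and 12.4; SAP 4.5).

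**Formula.** For x alive out of n, the exact (Clopper-Pearson) lower bound is the 0.05 quantile of a Beta(x, n − x + 1) distribution. Type I error and power are the binomial probabilities of reaching the minimum passing count at the goal and at the expected rate.

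**Reproducing the plan's figure at n = 57.**
- 6 months: at least 46 alive, bound 0.7008, type I error 0.0486, power 0.862.
- 24 months: at least 37 alive, bound 0.5322, type I error 0.0397, power 0.837.

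Both agree with the stated design (one-sided 0.05, power above 80%).

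**Effect on a borderline result.** Suppose k of 60 subjects are lost or withdrawn while on the pump and are then documented dead by the endpoint day. The documents give no value for k. The range 0 to 3 is an assumption, and 3 is the plan's allowance for attrition of every kind. The first figure in each cell takes the minimum passing count with these subjects excluded; the second keeps the same number alive and counts the k deaths as failures.

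| k | 6 months: excluded → counted | 24 months: excluded → counted |
|---|---|---|
| 0 | 49/60, 0.715 | 39/60, 0.536 |
| 1 | 48/59, 0.710 → 48/60, 0.696 | 38/59, 0.529 → 38/60, 0.519 |
| 2 | 47/58, 0.706 → 47/60, 0.678 | 38/58, 0.540 → 38/60, 0.519 |
| 3 | 46/57, 0.701 → 46/60, 0.660 | 37/57, 0.532 → 37/60, 0.502 |

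From k = 1 a pass becomes a fail at both time points. The k = 1 contrasts also hold under the two-decimal rounding in Appendix 4 (0.71 against 0.70 at 6 months; 0.53 against 0.52 at 24 months, reading the code's threshold as 0.525). At k = 3 the 6-month bound of 0.7008 passes only unrounded.

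**Away from the borderline.** The expected rates give 0.85 × 57 = 48.5 and 0.70 × 57 = 39.9 alive.
- 6 months: 48/57 still passes after two added deaths (48/59) but not three (48/60). 49/57 passes after three (49/60).
- 24 months: 40/57 passes after three, since 39/60 already passes.

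**Type I error.** Let true survival equal the goal p0, and let each of 60 subjects have probability f of being lost and then dead within the window. After exclusion the apparent survival is p0/(1 − f). Averaging the exact test over the binomial number excluded gives:

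| f | 6 months | 24 months |
|---|---|---|
| 0 | 0.030 | 0.034 |
| 1/60 | 0.053 | 0.050 |
| 2/60 | 0.083 | 0.065 |
| 3/60 | 0.121 | 0.083 |

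**The case against.** **The later-death rule may concern exposure only.** In both documents it follows a sentence on patient-years and follow-up time, and endpoint eligibility is set separately. That reading is open, so a flat contradiction over the proportions is not proven. It does not rescue the exclusion: the plan would then count exposure up to a known death on the pump while leaving that death out of the survival endpoint.

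**Time to death.** A reader of SAP 6.4.3.1 alone might infer that the death disappears from the Kaplan-Meier curve. The documents do not support that as settled. Appendix 4 codes all deaths as events, and SAP 7.3 keeps lost or withdrawn patients eligible for the overall survival analysis. What stands is an inconsistency.

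**Disposition.** SAP 8.1 counts patients who died before 24 months as having completed the study, which suggests that a death overrides the label. It governs the disposition table, however, and no endpoint section adopts it.

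**Sensitivity analysis.** Protocol 12.8 and SAP 8.7.5.1 impute failure where the primary endpoint cannot be assessed. This is supplementary, covers 6 months only, and is meant for unknown outcomes.

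**Size.** The flips are at minimum passing counts, and protocol 12.1 plans for ineligibility well under 5%. Both points stand.

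**Ascertainment.** Protocol 10.0 does not oblige investigators to seek events in former participants and asks only for those judged reasonably related. Counting deaths learned this way while lost survivors stay excluded biases survival downward. This stands as a cost of the fix.

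**Conclusion.** The concern holds for the two proportions: as written, a documented death by Day 183 or Day 730 is discarded if loss or withdrawal came first. For time to death, what holds is that the documents conflict.

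At the margin one subject decides the verdict at either time point. At the counts expected under the design rates, most such cases would not change it. The sizes rest on an assumed 0 to 3 such subjects of 60 and on the later-death rule's assumption that the subject was still on the pump.

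The direction applies to in-window deaths only. A subject lost before Day 183 whose death is dated after it was alive on that day, and excluding that subject lowers the estimate.

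A reader might infer that the CE Mark or labeling test is now at risk. The documents do not support this: SAP 5.2 has withdrawn the summary statistics, so the practical effect is small. The rules remain in the current text, and each case study still needs one outcome per subject.

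**What to change.** - **Eligibility.** In SAP 6.4.1, 6.4.2 and 7.3 and protocol 12.1, exclude a lost or withdrawn subject only when survival status at Day 183 (or Day 730) is unknown.
- **Failure.** Count a documented death on or before that day as an eligible failure when the subject was last known on MVAD support and consent permits use of the date.
- **Time to death.** Use the death date as the event for the same subjects, and align SAP 6.4.3.1 and Appendix 4 with protocol 12.6.
- **Case studies.** Apply the same rule to the outcome given for each subject.
- **Sensitivity.** If any summary is produced, also report the result under the present exclusion.

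The change is to wording. The estimate becomes slightly less favourable, and it is conservative, because deaths after loss are learned passively while lost survivors stay excluded. Removing that bias would require active follow-up of vital status.

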## 6.2 Time Point Algorithms

### 6.2.1 Relative Day

The date the device is implanted will be considered relative day 1, and the day before the device is implanted will be relative day -1. Relative days will be calculated as follows only when the full assessment date is known (i.e., partial dates will have missing relative days):

For days on or after the device is implanted:

Relative Study Day (Rel Day) = Date of Assessment – Date of implant + 1.

For days before the device is implanted:

Relative Study Day (Rel Day) = Date of Assessment – Date of implant.

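### SAP 7.3 moves partial dates to the earliest point, with no floor at the last date known alive and no end-date rule, and it conflicts with SAP 6.2.1 on relative days

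*SAP*

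**What the plan says.** SAP 7.3 opens its rule in general terms, "If a partial date is reported where the day is missing", and then states that "the day will be imputed as the first day of the month unless the month is the same month as the device is implanted"; in that month the implant day is used. For a missing month, "the month will be imputed to January unless the year is the same year as the device is implanted", when the implant month is used. Where both parts are missing, the same steps apply. The section extends the rule by name to adverse event dates. It neither names nor exempts death dates, and it does not separate start dates from end dates.

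The same section does consider death against follow-up. For a patient on support at last known follow-up, it says that if "a later date of death exists, the date of death must be considered the last follow-up for that patient". SAP 6.4.3.1 uses the last contact date known alive, but only to censor patients who remain alive on the device.

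SAP 6.2.1 takes another line on incomplete dates: "partial dates will have missing relative days". The primary endpoint in SAP 6.4.1 is defined on relative day, its numerator being "the number of patients alive at Relative Study Day 183". For eligible patients whose endpoint cannot be assessed, "they will be excluded from both denominator and numerator for this analysis". SAP 6.4.2 repeats this structure at Day 730.

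**The concern.** Death on the pump is the only failure event in this trial. Its date sets the time to death and may bear on the Day 183 and Day 730 status. A rule that always picks the earliest possible date, with no check against what is already known, can produce a death date that the trial's own visit records contradict. For end dates the earliest choice is the wrong direction, because it can place the end of an event before its start.

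The two SAP sections also give a programmer different instructions for the same record. Under 7.3 the partial date is completed. Under 6.2.1 it has no relative day. The first dates deaths too early, which works against the device. If the second leads to the subject being called not assessable, a known death leaves the primary analysis, which favours the device. The SAP does not say which section governs.

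**Working it through.** **Inputs.** Partial-date rule: SAP 7.3. Relative day and time to death, both date minus implant date plus 1: SAP 6.2.1 and 6.4.3.1. Cut-offs Day 183 and Day 730: SAP 6.4.1 and 6.4.2. Goal 70%, expected survival 85%, N = 57, one-sided 0.05: SAP 4.5. Planned implants from the second to the fourth quarter of 2015: protocol 6.2.

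**1. The plan's own figure.** The exact one-sided 95% lower bound for x survivors of n is the 0.05 quantile of Beta(x, n − x + 1).
- 45/57 gives 0.6813 and 46/57 gives 0.7008, so 46 survivors are needed.
- At that threshold the exact alpha is 0.0486 and the power at 85% is 86.2%. The stated power above 80% is reproduced.
- With 60 subjects, 49 are needed and power is 81.9%.

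The date rule does not affect N or power.

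**2. Time to death, day missing.** Implant on 15 July 2015.
- From implant to 31 December is 16 + 31 + 30 + 31 + 30 + 31 = 169 days, so 1 January 2016 is Day 171.
- 13 January is Day 183 and 18 January is Day 188.
- The subject is seen alive on 18 January and the death is recorded only as January 2016. SAP 7.3 gives 1 January, Day 171.
- The derived death is 188 − 171 = 17 days before a documented live contact. Floored at that contact, it is Day 188.

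Outside the implant month, the error for a missing day is at most 31 − 1 = 30 days.

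**3. Time to death, month and day missing.** Here the two rules are applied in turn.
- Same implant date, seen alive 30 November 2016 (Day 505), death recorded only as 2016: the rule gives 1 January 2016, Day 171. Floored, it is Day 505.
- In the implant year the result is the implant date itself. Implant 20 April 2015 and true death 20 December 2015 (Day 245) becomes Day 1.

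**4. End dates.** An adverse event starts on 20 March and its end is recorded only as March, with the implant in another month. The rule gives an end of 1 March, 19 days before onset.

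**5. Survival endpoints, if imputed dates feed the relative day.** The rule was applied to each of the 275 possible implant dates from 1 April to 31 December 2015.
- Day missing: some deaths after Day 183 are moved before it on 256 of the 275 implant dates (true death as late as Day 212).
- Month and day missing: 273 of 275 (true death as late as Day 547).
- Day missing, Day 730 cut-off: 257 of 275 (true death as late as Day 759).

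These are counts of possible dates, not of expected subjects.

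**6. Survival endpoints, if 6.2.1 governs.** The partial death date has no relative day. If the subject were then treated as not assessable, one known death would leave the denominator. For example, 46/58 (bound 0.6864) would become 46/57 (bound 0.7008).

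**7. How far one subject matters.** On the rule in SAP 8.7.1, 46/57 passes and 45/57 fails. The code in SAP Appendix 4 rounds the bound to two decimals before testing that it exceeds 0.70. Under that code 0.7008 becomes 0.70 and fails, so the step lies between 46 and 47 of 57, and the change in item 6 is from fail to fail.

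**The case against.** A reader might infer that a subject seen alive after Day 183 would be scored as dead before it. The documents do not support that. SAP 6.4.1 counts patients alive at Day 183, and a fully dated contact on Day 188 settles the matter whatever is done with the death date. SAP 6.2.1 also gives a partial date no relative day, and the sentence in 7.3 on a later date of death presumes that death follows last follow-up. Nor do the documents say that a missing relative day makes the endpoint not assessable. A death month wholly before Day 183 settles status too. If a subject were excluded, the sensitivity analysis in SAP 8.7.5.1 would count that subject as a failure.

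It would also be too much to say that every incomplete date goes to the first of the month or to January, since 7.3 has the implant-month and implant-year exceptions. Death dates are covered by the generality of the wording, not by name.

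The inputs should be rare. Protocol 14.3.1 requires deaths to reach the sponsor within 24 hours of knowledge, and protocol 15.2.2 provides for queries on missing data. No planned output uses adverse event durations. SAP 5.2 reports fewer than 15 subjects enrolled and withdraws summary statistics in favour of case studies, so the one-subject comparison above describes a test that is no longer planned.

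These points stand and limit the size of the finding. They do not remove it. The time-to-death formula uses calendar dates, so 6.2.1 gives it no protection; 7.3 still has no floor and no end-date rule; and the two sections still disagree.

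**Conclusion.** The point holds in limited form. As written, SAP 7.3 can place a death before a documented live contact in the time-to-death derivation (Day 171 against Day 188 in the example) and can place an adverse event end before its onset. Whether it reaches the Day 183 and Day 730 endpoints cannot be settled from the text, because 6.2.1 and 7.3 conflict. False early failure and loss of a known death are each possible readings, and neither is established.

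The practical effect is small. Version 2.0 leaves 7.3 in place, and SAP 7.1 still calls for listings of derived variables, so the exposure now is mainly wrong derived dates in listings and case narratives. The examples assume implants within the planned 2015 window and, where month and day are both missing, that the two rules are applied in turn.

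**What to change.** In SAP 7.3:
- Set an imputed death date to the later of the rule's date and the last date known alive, kept within the reported month or year. The floor should be that date itself: using the following day would move a subject seen alive on 31 July, with death reported in July, into August.
- Score Day 183 and Day 730 from fully dated contacts wherever these settle status.
- Impute end dates to the last day of the month, or to 31 December if the month is missing, capped at death, explant or last contact and never before onset.

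In SAP 6.2.1, state that the imputed death date is used for survival status and time to death.

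The cost is a few sentences of SAP wording and minor programming. Sample size, power and data collection do not change.
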